6 INCLUSION

Prior to the inclusion of any new patients in the IFCT-1601 IONESCO trial, the site should first submit by e-mail to [contact] the reports of initial CT scan and PET scan as well as the report of the multidisciplinary meeting if possible. A review of the imaging will take place by the steering committee if there is any doubt about the eligibility of the patient. Validation of the inclusion of the new patient will be sent to the site as soon as possible.

7 PRE-TREATMENT EVALUATION

Investigations		Timing
History and Physical Exam including:	
 • history including cigarette smoking • physical examination including height, weight, pulse, blood pressure • performance status • Concomitant medication 	Within 14 days prior to inclusion
Haematology	
 • CBC including haemoglobin, differential leukocyte, platelet count 	Within 14 days prior to inclusion
Biochemistry	
 • AST (SGOT) and ALT (SGPT) • Alkaline phosphatase • Total bilirubin (if total bilirubin is $\geq 2xULN$ (and no evidence of Gilbert's syndrome) then fractionate into direct and indirect bilirubin • Gamma glutamyltransferase • albumin • creatinine • Urea • CRP • TSH¹ • INR/APTT • Lactate dehydrogenase • Uric acid • Lipase • Amylase (if lipase > 2,5N) • Magnesium • Potassium • Bicarbonate sodium • Calcium • Chloride • Total protein 	Within 14 days prior to inclusion
	
 • HIV antibody • Hepatitis A antibody, • Hepatitis B surface antigen • Hepatitis C antibody 	

Radiology	
 • baseline CT chest and upper abdomen (must include adrenal glands) ² 	Within 28 days prior to inclusion
	
 • MRI or CT of brain • PET scan 	Within 28 days prior to inclusion
	
 • other baseline imaging (e.g. bone scan) 	Required, within 28 days of inclusion, only if suspicious signs/symptoms are present
Other Investigations	
 • ECG 	Within 2 months prior to inclusion if clinically indicated
	
 • urinalysis • lung function tests: FEV1, FVC, TLCO and SaO2 on room air • pregnancy test if applicable 	Within 2 months prior to inclusion
	
 • LVEF ³ 	Within 12 weeks prior to inclusion
	
 • Serum, plasma for correlatives • Feces • Tumor block available 	Prior to Cycle 1, day 1 dosing ⁴

1 If TSH is abnormal, both T3 and T4 should be measured (both are recommended but at least one of T3 or T4 is mandatory if TSH is abnormal).

2 Must be contrast enhanced CT scan; low dose surveillance CT is not acceptable. To ensure comparability, the baseline scans and subsequent scans to assess response must be performed using identical techniques (i.e. scans performed immediately following bolus contrast administration using a standard volume of contrast, the identical contrast agent, and preferably the same scanner). CT appearance consistent with post-operative change is expected and does not preclude inclusion.

3 MUGA or ECHO, only for patients with significant cardiac history.

4 Serum, plasma and feces for correlatives must be taken after consent is obtained but prior to day 1 dosing of cycle 1 - may be done after inclusion providing it is done prior to day 1 dosing or within 14 days prior to inclusion.

8 TREATMENT PLAN

The responsibility for treatment of patients rests with the individual investigator. Protocol treatment is to begin within 7 working days of inclusion.

8.1 Drug Administration

Agent(s)	Route	Duration	Dose and Schedule**
durvalumab	IV	60 minutes*	750 mg***on weeks 0, 2, 4

* See Section 7.5.1 for duration in the case of an infusion reaction.
** From inclusion.
*** Two week interval between infusions must be maintained; if infusion cannot be administered, it should be omitted until the next planned infusion.

Do not administer durvalumab unless treatment day tests meet the following criteria:

Haemoglobin ≥ 9 g/dL

Absolute neutrophil count $\geq 1.0 \times 10^9/L$

Platelets $\geq 100 \times 10^9/L$

Liver function tests \leq grade 1 or as per Section 7.5.4

All other related adverse events should be \leq grade 2. See Section 7.5.4 for additional details.

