8.4 Dose Adjustments

The major toxic effects of durvalumab which are anticipated to limit dosing are hypersensitivity/ infusion related reactions and possible class related immune related AEs, based on the mechanism of action of durvalumab leading to T-cell activation and proliferation. Potential immune related AEs include enterocolitis, dermatitis, hepatitis, pneumonitis and endocrinopathies [*Brahmer 2010; Hodi 2010*]. Patients should be monitored for signs and symptoms of immune related AEs. In the absence of an alternate aetiology (e.g. infection or relapse) signs or symptoms of enterocolitis, dermatitis, hepatitis, and endocrinopathy should be considered to be immune-related.

The guidelines which follow outline dose adjustments for several of these toxic effects. If a patient experiences several adverse events and there are conflicting recommendations, please use the recommended dose adjustment that requires the greatest dose hold or discontinuation (see Appendix II). Adverse events will be graded using the NCI Common Terminology Criteria for Adverse Events (CTCAE) (see Appendix III).

Dose reductions are not permitted, but dose adjustments (slowing/interruption of infusion rate, omission of a dose, or permanent discontinuation) will be made for hematologic and other adverse events.

If the infusion cannot be administered, it should be omitted until the next planned infusion.

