8.5 Management of Toxicity

The following general guidance should be followed for management of toxicities (see Appendix II):

1. Treat each of the toxicities with maximum supportive care (including slowing / interrupting / omitting the agent suspected of causing the toxicity where required).
2. If the symptoms promptly resolve with supportive care, consideration should be given to continuing the same dose of durvalumab along with appropriate continuing supportive care.

In addition to the dose adjustments shown in Section 7.4, the following are recommended:

- Patient evaluation to identify any alternative aetiology.

- In the absence of a clear alternative aetiology, all events of an inflammatory nature should be considered to be immune-related.
- Symptomatic and topical therapy should be considered for low-grade events.
- Systemic corticosteroids should be considered for a persistent low-grade event or for a severe event.
- More potent immunosuppressives should be considered for events not responding to systemic steroids.

Investigators should exercise clinical judgment in managing actual patients alongside the guidelines presented in the protocol(s). An event that exhibits rapid progression and/or the likelihood for high morbidity/mortality requires that clinical judgment be exercised above and beyond toxicity management guidelines to ensure that treatment is optimally tailored to any given patient's specific case. For example, the general principles outlined in the toxicity management guidelines describe prompt initiation of corticosteroids for both Grade 2 events (that have persisted for 4-5 days) and Grade 3-4 events; clinical judgment applied to this baseline guidance for an event that exhibits rapid progression and/or the likelihood for high morbidity/mortality - such as myocarditis - would warrant prompt initiation of high-dose corticosteroids without delay even for grade 2 cases. Similarly, clinical judgment for patients with suspected myocarditis should lead investigators to obtain a cardiology consult and institute a thorough diagnostic work-up (that includes exclusion of other alternate causes such as infection), and the appropriate management that includes discontinuing drug (permanently if biopsy-proven immune-mediated myocarditis) and, as already noted, the prompt use of steroids or other immunosuppressives.

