	
Grade 1 No dose modification
 
Grade 2 Hold study drug/study regimen dose until grade 2 resolution to \leq Grade 1
 
 • If toxicity worsens then treat as Grade 3 or Grade 4 • If toxicity improves to baseline then treat at next scheduled treatment date 
Study drug/study treatment can be resumed at the next scheduled dose once event stabilizes to grade ≤ 1 and 5-7 days have passed after completion of steroid taper
 
Patients with endocrinopathies who may require prolonged or continued steroid replacement can be retreated with study drug/study regimen on the following conditions: 1) the event stabilizes and is controlled , 2) the patient is clinically stable as per Investigator or treating physician’s clinical judgement, and 3) doses of prednisone are at less than or equal to 10mg/day or equivalent.
	
 - Symptomatic and topical therapy should be considered for low-grade (Grade 1 or 2, unless otherwise specified) events - For persistent (greater than 3 to 5 days) low-grade (Grade 2) or severe (Grade ≥ 3) events promptly start prednisone PO 1-2mg/kg/day or IV equivalent - Some events with high likelihood for morbidity and/or mortality - e.g., myo-carditis, or other similar events even if they are not currently noted in the guidelines - should progress rapidly to high dose IV corticosteroids (methylprednisolone at 2 to 4 mg/kg/day) even if the event is Grade 2, and if clinical suspicion is high and/or there has been clinical confirmation. Consider, as necessary, discussing with the study physician, and promptly pursue specialist consultation. - If symptoms recur or worsen during corticosteroid tapering (28 days of taper), increase the corticosteroid dose (prednisone dose [e.g. up to 2-4mg/kg/day or IV equivalent]) until stabilization or improvement of symptoms, then resume corticosteroid tapering at a slower rate (≥ 28 days of taper)

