	Grade 2 (Symptomatic, medical intervention indicated, limiting instrumental ADL)	
Hold study drug/study regimen dose until grade 2 resolution to \leq Grade 1
 
 • If toxicity worsens then treat as Grade 3 or Grade 4 • If toxicity improves to baseline then the decision to reinitiate study drug/regimen at next scheduled treatment date will be based upon treating physician's clinical judgment. 
Study drug/study treatment can be resumed at the next scheduled dose once event stabilizes to grade \leq1 and 5-7 days have passed after completion of steroid taper
	
For Grade 2 (Mild to Moderate New Symptoms)
 
 - Monitor symptoms daily and consider hospitalization - Promptly start systemic steroids (e.g., prednisone 1-2mg/kg/day or IV equivalent) - Reimaging as clinically indicated - If no improvement within 3-5 days, additional workup should be considered and prompt treatment with IV methylprednisolone 2-4mg/kg/day started - If still no improvement within 3-5 days despite IV methylprednisolone at 2-4/g/kg/day, promptly start immunosuppressive therapy such as TNF inhibitors (e.g. infliximab at 5mg/kg every 2 weeks). Caution: Important to rule out sepsis and refer to infliximab label for general guidance before using infliximab - Once improving, gradually taper steroids over \geq4 weeks and consider prophylactic antibiotics, antifungal or anti-PJP treatment (refer to current NCCN guidelines for treatment of cancer-related infections)

			
[Category 2B recommendation)]¹²³
 
 - Consider pulmonary and infectious disease consult - Consider as necessary discussing with study physician

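### Section 8.1's treatment-day limit of grade 2 for related non-liver adverse events does not match Appendix II: it is looser for most events and stricter for a few, and the section it cites does not exist

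*Protocol*

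**What the plan says.** Section 8.1 introduces its list with "Do not administer durvalumab unless treatment day tests meet the following criteria". It then gives limits for haemoglobin, neutrophils and platelets, a liver-test limit of grade 1 or as per Section 7.5.4, and finally: "All other related adverse events should be \leq grade 2. See Section 7.5.4 for additional details".

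Section 8.4 refers to Appendix II and gives a tie-break, the greatest hold or discontinuation, which opens: "If a patient experiences several adverse events and there are conflicting recommendations". Section 8.5 says: "The following general guidance should be followed for management of toxicities (see Appendix II".

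Appendix II sets dose rules by event and grade. Its general rule for a grade 2 immune-mediated event reads "Hold study drug/study regimen dose until grade 2 resolution to" grade 1 or lower. For grade 2 pneumonitis it applies the same hold and adds "Promptly start systemic steroids (e.g., prednisone 1-2mg/kg/day or IV equivalent", then "Once improving, gradually taper steroids over" at least 4 weeks. Dosing may resume at the next scheduled dose once the event is at grade 1 or lower and 5 to 7 days have passed since the taper ended.

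Sections 4 and 8.1 plan three infusions, on days 1, 15 and 29. Section 8.6 does not extend treatment for omitted doses. Section 10.1 places surgery no later than 6 weeks after the first infusion and requires all adverse events to be at grade 1 or lower beforehand.

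**The concern.** Section 8.1 is the list a site checks on the day of an infusion. Its liver line is set at grade 1 and its line for everything else at grade 2, so grade 2 reads as a deliberate limit for non-liver toxicity. Used by itself, the list would not stop a further dose of PD-L1 antibody in a patient with grade 2 pneumonitis, within weeks of a planned lung resection, although Appendix II requires a hold. The line's only pointer to further detail leads nowhere.

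What is at stake is consistent dosing and the safety of individual patients. The type I error, power and sample size are not touched.

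**Working it through.** No statistical formula applies. The check is a comparison of texts, a count, and a date calculation.

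**1. Grade 2 rule in each non-liver block of Appendix II** (the two hepatitis blocks are left out)

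| Block | Rule at grade 2 |
|---|---|
| Immune-mediated, general | hold to grade 1 or lower |
| Pneumonitis/ILD | hold to grade 1 or lower |
| Diarrhea/colitis | hold to grade 1 or lower |
| Nephritis/creatinine | hold to grade 1 or lower, or baseline |
| Peripheral neuromotor syndromes | hold to grade 1 or lower |
| Myocarditis | hold to grade 0 |
| Myositis/polymyositis | hold to grade 1 or lower |
| Non-immune-mediated (related events) | hold to grade 1 or lower, or baseline |
| Rash | hold only if persistent beyond 1–2 weeks |
| Endocrinopathy | hold until stable, except hypothyroidism and type 1 diabetes |
| Neurotoxicity | hold if acute motor; hold only considered if sensory |
| Infusion-related reaction | no hold; rate slowed or infusion interrupted |

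Count: 8 hold, 3 hold in part, 1 does not hold; 8/12 = 67%. With the nine named organ blocks only (general, non-immune and infusion-reaction blocks dropped), 6 hold: 6/9 = 67%.

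**2. Where Appendix II is looser than 8.1**

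- Isolated hypothyroidism and type 1 diabetes at grade 3 or 4 are treated without interrupting the drug.
- Other grade 3–4 endocrinopathies may resume once stable and the steroid taper is complete.
- Asymptomatic amylase or lipase elevation of grade 3 or higher is held, then may continue or resume if the work-up shows no pancreatitis.
- Grade 3–4 inflammatory reactions attributed to local tumour response do not oblige the site to stop.

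If such an event is related and still above grade 2 on the day, the 8.1 line forbids the dose. Appendix II also allows a non-immune grade 3 event that falls to grade 2 within 7 days to resume at the next dose. This agrees with 8.1 and shows that some dosing at grade 2 is intended.

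**3. The reference**

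Section 7 is the pre-treatment evaluation and has no numbered subsections. Shifted by one chapter, the target would be 8.5.4, but Section 8.5 has no numbered subsections either. Both mentions of 7.5.4 in Section 8.1 therefore fail.

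**4. Worked example: grade 2 pneumonitis present on day 15**

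- Steroids start on day 15. A taper of at least 4 weeks ends no earlier than 15 + 28 = day 43.
- Adding 5 to 7 days, the earliest resumption is day 48 to 50.
- Last planned infusion: day 29. Latest planned surgery: 1 + 42 = day 43.
- Since 48 > 43 > 29, Appendix II gives 1 infusion. Section 8.1 alone would let through up to 3, provided the event is still no worse than grade 2 on day 29.
- If the event is first present on day 29: 2 infusions against 3.

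This is close to the largest possible difference. Under the general immune rule, steroids at grade 2 come only if the event lasts: "For persistent (greater than 3 to 5 days) low-grade (Grade 2) or severe". An event that resolves without steroids may cost one infusion or none.

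**The case against.** The strongest reply is that nothing in the protocol tells a site to infuse at grade 2. Section 8.1 is phrased as a prohibition: its conditions must be met, but meeting them authorises nothing, and every hold in Appendix II still applies. Sections 8.4 and 8.5 lead to Appendix II, and Section 13.1 names it for unacceptable toxicity. Section 8.5 itself says that management of suspected myocarditis includes discontinuing the drug, and it considers continuing the same dose only if symptoms resolve promptly. On this view grade 2 is an outer ceiling with event-specific rules beneath it, and 7.5.4 is one of several references left one chapter behind.

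Most of this stands. A reader might infer that the protocol permits infusion at grade 2 pneumonitis or myocarditis, or that 8.1 is simply the looser text. The documents support neither: a site applying both texts would hold, and for some events 8.1 is the stricter text.

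The ceiling reading does not remove the mismatch, because Appendix II goes above that ceiling for the events in step 2. Section 8.1 does not name Appendix II, and no sentence says which text governs. The tie-break in Section 8.4 is worded for several events in one patient, not for one event under two limits.

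**Conclusion.** The point holds as an inconsistency in a safety-relevant dosing rule. The 8.1 limit is looser than Appendix II in 8 of 12 non-liver blocks, stricter for a few events at grade 3 or 4, and supported by a reference to a section that does not exist. The exposure is confined to sites that rely on the 8.1 list alone.

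The 67% is a share of table blocks, not of events, patients or doses. The comparison of one infusion with up to three is a constructed case: it assumes steroids from day 15, the shortest permitted taper, and an event that stays at grade 2 or lower to day 29. The protocol gives no grade 2 rate, so no number of affected patients follows.

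A reader might also infer that patients could be operated on at grade 2. Section 10.1 rules that out by requiring grade 1 or lower before surgery. The primary analysis is unaffected. The correction should be made, but the point does not bear on whether the trial can answer its question.

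**What to change.** Replace the last line of the 8.1 list with: *All other related adverse events must be grade 1 or lower, or at baseline, except where Appendix II expressly permits dosing or resumption at a higher grade; where Appendix II requires a stricter threshold (for example grade 0 for myocarditis), Appendix II applies.* This keeps Appendix II's allowances in both directions. A plain rule that the stricter text always wins would cancel them, for example for isolated hypothyroidism.

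Replace both references to 7.5.4 in Section 8.1 with *Section 8.5 and Appendix II*. Correct the 7.5.1 reference under the 8.1 dosing table as well; infusion reactions are now covered in Section 8.3.1 and Appendix II. The other outdated chapter 7 references, for example in Sections 8.2, 8.5, 8.8.1 and 13.1, can be renumbered in the same pass.

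The cost is amendment wording only, with no extra visits, tests or patients.

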8.2 Premedication

Premedication is not expected to be required. See Section 7.5.1 with respect to premedication of patients that have had a prior \leq Grade 2 infusion-related reaction.

8.3 Patient Monitoring

8.3.1 Monitoring of dose administration

Subjects will be monitored before, during and after the infusion with assessment of vital signs at the times specified in the Schedule of Assessment. Subjects are monitored (pulse rate, blood pressure) every 30 minutes during the infusion period (including times where infusion rate is slowed or temporarily stopped).

In the event of a \leq Grade 2 infusion-related reaction, the infusion rate of study drug may be decreased by 50% or interrupted until resolution of the event (up to 4 hours) and re-initiated at 50% of the initial rate until completion of the infusion. For subjects with a \leq Grade 2 infusion-related reaction, subsequent infusions may be administered at 50% of the initial rate. Acetaminophen and/or an antihistamine (e.g., diphenhydramine) or equivalent medications per institutional standard may be administered at the discretion of the investigator. If the infusion-related reaction is Grade 3 or higher in severity, study drug

will be discontinued. The standard infusion time is one hour, however if there are interruptions during infusion, the total allowed time from infusion start to completion of infusion should not exceed 4 hours at room temperature, with maximum total time at room temperature not exceeding 4 hours (otherwise requires new infusion preparation).

As with any antibody, allergic reactions to dose administration are possible. Appropriate drugs and medical equipment to treat acute anaphylactic reactions must be immediately available, and study personnel must be trained to recognize and treat anaphylaxis. The study site must have immediate access to emergency resuscitation teams and equipment in addition to the ability to admit subjects to an intensive care unit if necessary.

Patients will be monitored during the infusion and for a 30 minute observation period after the infusion with assessment of vital signs as per local procedures.

All patients should be closely monitored according to guidelines in Section 8 and be advised to contact the treating centre in the case of significant toxicities.

8.4 Dose Adjustments

The major toxic effects of durvalumab which are anticipated to limit dosing are hypersensitivity/ infusion related reactions and possible class related immune related AEs, based on the mechanism of action of durvalumab leading to T-cell activation and proliferation. Potential immune related AEs include enterocolitis, dermatitis, hepatitis, pneumonitis and endocrinopathies [*Brahmer 2010; Hodi 2010*]. Patients should be monitored for signs and symptoms of immune related AEs. In the absence of an alternate aetiology (e.g. infection or relapse) signs or symptoms of enterocolitis, dermatitis, hepatitis, and endocrinopathy should be considered to be immune-related.

The guidelines which follow outline dose adjustments for several of these toxic effects. If a patient experiences several adverse events and there are conflicting recommendations, please use the recommended dose adjustment that requires the greatest dose hold or discontinuation (see Appendix II). Adverse events will be graded using the NCI Common Terminology Criteria for Adverse Events (CTCAE) (see Appendix III).

Dose reductions are not permitted, but dose adjustments (slowing/interruption of infusion rate, omission of a dose, or permanent discontinuation) will be made for hematologic and other adverse events.

If the infusion cannot be administered, it should be omitted until the next planned infusion.

8.5 Management of Toxicity

The following general guidance should be followed for management of toxicities (see Appendix II):

1. Treat each of the toxicities with maximum supportive care (including slowing / interrupting / omitting the agent suspected of causing the toxicity where required).
2. If the symptoms promptly resolve with supportive care, consideration should be given to continuing the same dose of durvalumab along with appropriate continuing supportive care.

In addition to the dose adjustments shown in Section 7.4, the following are recommended:

- Patient evaluation to identify any alternative aetiology.

- In the absence of a clear alternative aetiology, all events of an inflammatory nature should be considered to be immune-related.
- Symptomatic and topical therapy should be considered for low-grade events.
- Systemic corticosteroids should be considered for a persistent low-grade event or for a severe event.
- More potent immunosuppressives should be considered for events not responding to systemic steroids.

Investigators should exercise clinical judgment in managing actual patients alongside the guidelines presented in the protocol(s). An event that exhibits rapid progression and/or the likelihood for high morbidity/mortality requires that clinical judgment be exercised above and beyond toxicity management guidelines to ensure that treatment is optimally tailored to any given patient's specific case. For example, the general principles outlined in the toxicity management guidelines describe prompt initiation of corticosteroids for both Grade 2 events (that have persisted for 4-5 days) and Grade 3-4 events; clinical judgment applied to this baseline guidance for an event that exhibits rapid progression and/or the likelihood for high morbidity/mortality - such as myocarditis - would warrant prompt initiation of high-dose corticosteroids without delay even for grade 2 cases. Similarly, clinical judgment for patients with suspected myocarditis should lead investigators to obtain a cardiology consult and institute a thorough diagnostic work-up (that includes exclusion of other alternate causes such as infection), and the appropriate management that includes discontinuing drug (permanently if biopsy-proven immune-mediated myocarditis) and, as already noted, the prompt use of steroids or other immunosuppressives.

